### **Phase 2 Sample Size Calculation for the Cohort Where Loncastuximab Tesirine is Given at Every Cycle in Combination with Ibrutinib**

The primary hypothesis is that the CRR is based on central review for patients treated with the re-determined RP2D of loncastuximab tesirine and ibrutinib combination is significantly greater than 30% (i.e.,  $H_0: p \leq 0.3$  vs.  $H_a: p > 0.3$ ). This hypothesis will be tested at type I error of 0.05 (two sided).

A two-stage design with futility monitoring (Zeng et al., 2015) will be used. The null hypothesis that the true CRR is 0.3 will be tested against a one-sided alternative. In the first stage, 60 patients will be accrued. If there are 20 or fewer CRs in these 60 patients, this cohort will be stopped. Otherwise, 40 additional patients will be accrued for a total of 100. The null hypothesis will be rejected if 40 or more CRs are observed in 100 patients. This design yields a type I error rate of 0.05 and power of 85% when the true CRR is 0.45. Enrollment will continue during the interim analysis.

## **4.2 Randomization**

Not applicable.

## **4.3 Modifications to the statistical section of the protocol**

Not applicable.

## 5 Statistical methods

All analyses will use SAS® version 9.4 or higher.

Unless otherwise stated, tables, listings, and figures will be broken down by cohort (non-GCB DLBCL, GCB DLBCL, all DLBCL and MCL). Additional tables include Phase 1 tables by dose level for safety, demographic and dosing, Phase 1 tables by dose level for dose escalation patients only, and tables of 60 µg/kg and 75 µg/kg loncastuximab tesirine in both Phase 1 and 2 by cohort. Tables and figures are based on the defined analysis population.

Categorical data will be presented using counts and percentages, with the number of patients in the analysis population as the denominator for percentages. Percentages will be rounded to 1 decimal place and not be displayed for zero counts.

Continuous data will be summarized using the number of observations (n), mean, standard deviation (std), median, minimum, and maximum. Minima and maxima will be rounded to the precision of the original value, and means, medians, and 95% confidence intervals (CIs) if presented will be rounded to 1 decimal place greater than the precision of the original value. The std will be rounded to 2 decimal places greater than the precision of the original value, up to a maximum of 3 decimal places.

CI will be two-sided and use  $\alpha=0.05$  (i.e., 95% CIs), unless otherwise specified. For exact estimates, the CI will be calculated using the Clopper-Pearson exact method. For Kaplan-Meier estimates, the CI will be calculated using the Greenwood's formula with (complementary) log-log transformation.

Kaplan-Meier plots will be provided along with Kaplan-Meier estimates.

The Baseline value is defined as the last non-missing value or measurement taken prior to the first dose of study drug.

### 5.1 Analysis Populations

#### 5.1.1 Safety Analysis Set

All patients who receive study drugs.

#### 5.1.2 DLT-evaluable Analysis Set

All patients in Phase 1 dose escalation, who receive study drugs, excluding patients who discontinue from the study during the dose limiting toxicity (DLT) period without experiencing a DLT.

[figure not shown]

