This is a Phase 1/2 open-label single-arm combination study, with a dose escalation Phase 1 followed by Phase 2. The study will enroll approximately 243 patients.

Phase 1:

A standard 3+3 dose escalation design will be used. The DLT Period will be the 21 days following the first dose of ibrutinib. The dose escalation cohort will receive loncastuximab tesirine for 2 cycles with concurrent ibrutinib (concomitant therapy) and may then continue ibrutinib therapy

up to 1 year. An additional dose level of 75 μ g/kg loncastuximab tesirine may be explored and evaluated during this phase of the study.

A DESC composed of study investigators and ADC Therapeutics personnel will be responsible for decisions concerning dose escalation. When the maximum tolerated dose (MTD) or Recommended Phase 2 Dose (RP2D) is defined there will be an efficacy and safety evaluation made by the Sponsor in consultation with investigators to determine benefit risk of the combination therapy.

Once MTD or RP2D is determined and if there is a $\geq 10\%$ improvement observed in CRR or ORR in any of the treatment cohorts in all DLBCL, non-GCB, GCB, or MCL when compared to the loncastuximab tesirine monotherapy, along with an acceptable safety profile, then Phase 2 of the study will commence.

Phase 2:

Once the dose level of loncastuximab tesirine has been defined, the Phase 2 portion of the study planned to enroll in 3 separate cohorts: non-GCB DLBCL, GCB DLBCL, and MCL.

In the non-GCB DLBCL cohort, a Simon's 2-stage design will be used with an interim analysis for futility on the first 22 patients. If ≥ 6 patients achieve CR, this cohort will proceed to complete full enrollment. Enrollment will continue during the interim analysis; however, further enrollment in this cohort will be halted if futility is confirmed.

As of the data cutoff April 21, 2021, the interim analysis for Non-GCB and GCB DLBCL cohorts was performed and the futility on non-GCB DLBCL was not met.

Subsequent to the interim analysis showing the potential of every cycle dosing of loncastuximab tesirine (see [Section 2.2](#)), the following will be performed:

- RP2D will be re-determined by DESC
- Enrollment of the non-GCB DLBCL cohort treated with the combination of loncastuximab tesirine administered at an intermittent dose schedule and daily ibrutinib will be closed. GCB and MCL will complete the enrollment target set forth in the initial phase 2 design and remain under the initial treatment schedule.

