6.4 Dose Escalation

6.4.1 Dose Escalation Design

The dose escalation of loncastuximab tesirine in Phase 1 will follow a standard 3+3 design using the dose levels defined in [Section 6.5](#). The dose one dose level below the dose at which ≥33% of patients experience a DLT will be considered the MTD. Cohorts of 3 patients will be treated, starting at the initial dose level. If 0 of 3 patients in the first cohort at any dose level experience a DLT, then the following cohort will be treated at the next higher dose level. If 2 of 3 patients experience a DLT, then the preceding dose level will be determined as the MTD. If 1 of 3 patients experiences a DLT, then 3 additional patients will be treated at that dose level. If 0 of the 3 additional patients experience a DLT, then the following cohort will be treated at the next higher

dose level. If 1 or more of the 3 additional patients experience a DLT, then the preceding dose level will be determined as the MTD.

There will be a minimum of 5 days between dosing the first and second patient at each dose level during dose escalation.

Patients who discontinue from the study prior to completion of the DLT Period without a DLT will be replaced.

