6.4.2 Dose-Limiting Toxicity Period

The first 21 days of ibrutinib administration will be considered the DLT Period for patients in Phase 1 dose escalation who are following the 3+3 study design.

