7.1 Discontinuation from Study Treatment

A patient may be discontinued from study treatment for any of the following reasons:

- Disease progression
- Unacceptable toxicity
- Patient decision
- Transplant therapy
- Major protocol deviation
- The Investigator determines that it is in the best interest of the patient to discontinue the patient's participation in the study.
- Discontinuation of the study by the Sponsor
- Pregnancy
- Death

IMPORTANT: Study treatment discontinuation is not to be automatically considered as withdrawal from the study. Patients discontinuing study treatment will be asked to perform an EOT visit ([Section 4.4](#)) and continue with the Follow-up Period ([Section 4.5](#)) as per protocol.

The investigational site should make every effort to complete follow-up per protocol. If patients are unable to return to the site, patient status, including but not limited to survival status, may be obtained by site staff via phone, email, or mail.

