9.2 Analysis Populations

- The Safety population will consist of all patients who receive study drug.
- The DLT-evaluable population will consist of all patients in Phase 1 dose escalation, who receive study drugs, and will exclude patients who discontinue from the study during the DLT Period without experiencing a DLT.
- The Efficacy population will consist of all patients who receive at least 1 dose of study drug, who have valid baseline disease assessment(s), and who have at least one valid post-baseline disease assessment. Patients who do not have a post-baseline assessment due to early clinical progression or death (after receiving study drug) will also be included.
- The PK population will consist of all patients who have at least 1 pre-(C1D1) and 1 post-dose valid PK assessment.
- [REDACTED]
- Per Protocol population: All patients in the Safety population without major protocol deviations, which will be further described in detail in the SAP.

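### The DLT-evaluable set and the replacement rule turn on leaving the study, so a patient who stops drug early with no recorded DLT still counts, which can lower the apparent DLT rate by an unknown amount

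*SAP*

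**What the plan says.** Three provisions use the same test. The SAP set consists of Phase 1 dose-escalation patients who received study drugs, "excluding patients who discontinue from the study during the dose limiting toxicity (DLT) period without experiencing a DLT". Protocol 9.2 says that the population "will exclude patients who discontinue from the study during the DLT Period without experiencing a DLT". Protocol 6.4.1 adds: "Patients who discontinue from the study prior to completion of the DLT Period without a DLT will be replaced".

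Protocol 7.1 then states: "Study treatment discontinuation is not to be automatically considered as withdrawal from the study". Such patients have an end-of-treatment (EOT) visit and go on to follow-up. No section sets a minimum exposure or a minimum period of safety observation for evaluability.

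The window is worded in two ways. Protocol 6.4.2 says: "The first 21 days of ibrutinib administration will be considered the DLT Period". The study design part of the protocol synopsis says: "The DLT Period will be the 21 days following the first dose of ibrutinib". The first can be read as 21 days on drug, the second as 21 calendar days.

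The decision rule is in protocol 6.4.1: "The dose one dose level below the dose at which ≥33% of patients experience a DLT will be considered the MTD". For a level that has one DLT in its first three patients: "If 1 or more of the 3 additional patients experience a DLT, then the preceding dose level will be determined as the MTD".

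**The concern.** DLT incidence is a Phase 1 primary endpoint, and finding the MTD or recommended dose is part of the Phase 1 primary objective (protocol Table 3). The DLT counts drive the 3+3 steps and also the limit of one DLT in six patients for expanding a dose level (protocol 2.1 and 4.1). SAP 5.10.1.2 tabulates DLTs by dose level on this set, and SAP 5 makes the analysis population the denominator for percentages.

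A patient who stops on, say, Day 8 and has no recorded DLT is evaluable under the text. Several DLTs are detected by laboratory tests: Grade 4 neutropenia of more than 7 days, Grade 4 thrombocytopenia, a Hy's law case (protocol 6.4.3). The Day 8 and Day 15 laboratory tests belong to the Treatment Period (protocol Table 1), and after EOT the visits are 12 weeks apart (protocol 4.5). Adverse event collection can also end early if new anticancer therapy starts (protocol 8.2.2). Partial exposure without a DLT is foreseeable too: protocol 6.5.2 requires an ibrutinib hold for any Grade 3 or higher toxicity, while 6.4.3 does not count certain Grade 3 events as DLTs.

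The direction is clear if any DLT risk goes unobserved. The apparent DLT rate falls, a level passes more easily, and dose selection is pushed upward.

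**Working it through.** **The plan's own figure.** The documents give no operating characteristics for the escalation. The one figure to reproduce is the 33% threshold. The smallest stopping result in six patients is 2/6 = 33.3%, and the largest passing result is 1/6 = 16.7%. The threshold and the rule agree.

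**Inputs.**
- The 3+3 rule of protocol 6.4.1: a level passes with 0/3, or with 1/3 followed by 0/3.
- True DLT rate p: illustrative values 0.20, 0.33 and 0.40.
- q, the share of patients who stop early but stay on study. Assumption: 10% or 20%.
- f, the share of those patients' DLT risk that goes unobserved or never arises because exposure was cut short. Assumption: 0 to 1.

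The documents give neither q nor f.

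**Formula.** With patients independent, the effective rate is r = p × (1 − q × f), and

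P(pass) = (1 − r)³ + 3r(1 − r)² × (1 − r)³.

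**Full observation, p = 0.33.** 0.67³ = 0.3008 and 3 × 0.33 × 0.67² = 0.4444, so P(pass) = 0.3008 + 0.4444 × 0.3008 = 0.434. The same value holds for any q when f = 0.

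**All risk lost (f = 1), p = 0.33.**
- q = 10%: r = 0.297 and P(pass) = 0.500.
- q = 20%: r = 0.264 and P(pass) = 0.570.

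| True rate p | Full observation, or f = 0 | q = 10%, f = 0.25 to 1 | q = 20%, f = 0.25 to 1 |
|---|---|---|---|
| 0.20 | 0.709 | 0.719 to 0.752 | 0.730 to 0.793 |
| 0.33 | 0.434 | 0.451 to 0.500 | 0.467 to 0.570 |
| 0.40 | 0.309 | 0.326 to 0.378 | 0.343 to 0.454 |

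**Exactly one early stopper among the first three, p = 0.33.** P(pass) is 0.471 (f = 0.25) to 0.582 (f = 1), against 0.434.

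**Reported rate.** One DLT with one early stopper counted among six is 1/6 = 16.7%. With that patient excluded it is 1/5 = 20.0%.

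**How large f can be.** Three provisions bear on this.
- Everyone in the set has received study drug. The escalated drug is a single Cycle 1 Day 1 infusion within the window, and the next dose has target Day 22 (SAP Table 1). An early stop therefore normally shortens only ibrutinib, which is given at one fixed dose across levels.
- Adverse events are collected for 30 days after the last dose. Even if the last dose is on Day 1, this runs to Day 1 + 30 = Day 31, past Day 21, unless new anticancer therapy starts first.
- The Dose Escalation Steering Committee (DESC) sets the MTD on safety findings as well as DLTs (protocol 6.4.4).

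These make f = 1 a worst case.

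**The case against.** The strongest reply is that the gap in the wording does little harm. No patient in the set is unexposed. A DLT that occurs in the window after drug is stopped still counts, because the DLT definition does not require the patient to be on drug. The EOT visit includes hematology and chemistry. The remaining gap is laboratory-only events between an early EOT and Day 21, events after early new therapy, and toxicity that the missed ibrutinib would have caused. All of this stands, and it is why the upper figures are bounds and not estimates.

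It can also be said that the decisions are largely past. Dose Levels 1 and 2 have completed enrollment (protocol 6.3.1), 60 µg/kg was chosen as the initial recommended dose (protocol 2.2), and SAP section 4 records that the study was discontinued and the every-cycle cohort will not be enrolled. This stands as well: new replacement patients are hardly a live remedy. The DLT table, including the 75 µg/kg level, is still to be reported.

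The last objection is that an exposure threshold set now is post hoc and could remove patients whose ibrutinib was held for toxicity that was not a DLT. That is correct, and it shapes the fix. It does not justify leaving incomplete observation invisible in the table.

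**Conclusion.** The point holds as a defect in the evaluability rule. As written, a patient with incomplete exposure or observation and no recorded DLT is evaluable and is not replaced. This can lower a Phase 1 primary output. At a true rate of 33%, the chance of passing rises from 0.434 by nothing at all (f = 0) up to a ceiling of 0.500 with 10% early stoppers or 0.570 with 20%. Both q and f are assumptions.

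A reader might go further in three ways that the documents do not support.
- That early stoppers automatically count as DLT-free with no DLT risk. They have received study drug, and their events are still collected.
- That the monotherapy median PFS of 2.83 to 4.93 months (protocol 1.2.2) shows how many stop within 21 days. An exponential curve would give 1 − 0.5^(0.69/4.93) = 9% to 1 − 0.5^(0.69/2.83) = 16%. But PFS events include deaths, which already count as leaving the study (protocol 7.2). The first scheduled scan on treatment is at Week 6, and progressing is not the same as stopping drug.
- That a dose was wrongly selected. Nothing shows that an early stopper occurred in the escalation, and the summary of Amendment 2 records two DLTs at 90 µg/kg, the level that was not taken forward.

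**What to change.** In SAP 5.1.2, and in protocol 9.2 and 6.4.1 if escalation continues, define DLT-evaluable as dose-escalation patients who either had a DLT, or completed the DLT period with the Cycle 1 infusion, a minimum share of planned ibrutinib set by the sponsor, and the scheduled safety assessments. Apply the same definition to replacement. Reconcile the synopsis and protocol 6.4.2 so that the 21-day window has a single definition. Do not drop patients whose shortfall was due to toxicity.

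For escalation already done, keep the DLT table on the existing set, since that is the set defined in the plan, and add the table on the new set as a sensitivity analysis. List patients who stopped or held either drug in the window, with reasons. If there are none, the two tables agree and the result is confirmed.

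The cost is some wording, one extra table and one listing. Listings of exposure and of DLTs are already planned (SAP 5.8.1 and 5.10.1.2). The downside is a possibly smaller DLT denominator and a threshold chosen after escalation, which is why the new set should stand beside the existing one and not replace it.

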#### 5.1.3 Efficacy Analysis Set

All patients who receive at least 1 dose of study drugs, have valid baseline disease assessment(s), and have at least one valid post-baseline disease assessment. Patients who do

not have a post-baseline assessment due to early clinical progression or death (after receiving study drugs) will also be included.

#### **5.1.4 Pharmacokinetics (PK) Analysis Set**

All patients who receive study drugs and have at least 1 pre-(C1D1) and 1 post-dose valid PK assessment.

#### **5.1.6 Per Protocol Set**

All patients in the Safety Analysis Set without major protocol deviations. More details are in Section 4.3.

### **5.2 Patient Disposition**

Enrolled subjects include all patients who signed informed consent forms. All subjects enrolled, including screen fails, will be summarized. Subjects who discontinued treatment and discontinued from the study will be summarized, along with the primary reasons for discontinuation. The disposition summary will be based on the Safety Analysis Set.

Patient disposition data will be listed.

### **5.3 Protocol Deviations**

All protocol deviations will be determined prior to database lock and will be agreed upon by a review of individual subject data. Major protocol deviation criteria will be established and subjects with major protocol deviations will be identified and documented before the database lock for the primary analysis.

The number and percentage of patients with any important clinical study report (CSR)-reportable protocol deviation will be summarized overall and by type of deviation. The pre-defined important CSR-reportable protocol deviations are listed below; in addition, any other protocol deviations deemed by ADCT medical to be important CSR-reportable deviations will be included in the summary.

1. Patient entered the study even though they did not satisfy the entry criteria
2. Patient received a prohibited concomitant treatment during the study
3. Patient who met criteria for mandatory study drug discontinuation during the study but did not have study drug withdrawn
4. Patient who received the wrong treatment or incorrect dose, including dose not specified in the protocol and actual dose of study drug was greater than 15% more or less than **protocol** planned dose.

Important protocol deviations will be summarized and listed.

## **5.4 Demographic and Baseline Characteristics**

Demographic and baseline characteristics will be tabulated for the Safety Analysis Set.

Demographic and baseline characteristics data will also be listed.

## **5.5 Cancer History and Medical History**

Cancer history, prior radiotherapy, prior cancer surgery, prior system treatments will be tabulated for the Safety Analysis Set.

Cancer history, medical history, prior radiotherapy, prior cancer surgery, and prior system treatments will be listed.

## **5.6 Stem Cell Transplant**

Stem cell transplant, including prior to study and on study, will be tabulated for the Safety Analysis Set.

Stem cell transplant will be listed.

## **5.7 Prior and Concomitant Medications (other than anticancer therapies)**

All medications will be recorded in the CRF starting from the ICF signature date or from 14 days prior to C1D1, whichever is earlier, and continuing until 30 days after last dose of study drug.

All medications will be coded using the World Health Organization-Drug Dictionary (WHO-DD) version 2019 March 01.

Prior and concomitant medications will be listed.

## **5.8 Exposure to Treatment**

### **5.8.1 Extent of Study Drug Exposure**

Study drug exposures will be based on the Safety Analysis Set.

A treatment cycle is defined as 3 weeks (i.e., 21 days) for Cycle 1 and Cycle 2, and then 4 weeks (i.e., 28 days) for subsequent cycles.

Duration of treatment (days) for loncastuximab tesirine, ibrutinib and both is calculated as date of last treatment – date of first treatment + 1.

### **Loncastuximab tesirine:**

Loncastuximab tesirine will be administered as a 30-minute IV infusion on C1D1 and C2D1 per the dose escalation plan.

During Phase 1, patients who have a response of PR or SD at the 14-week disease assessment may receive 2 additional doses of loncastuximab tesirine given 4 weeks apart (C5D1 and C6D1).

During Phase 2 when loncastuximab tesirine is given intermittently, patients who have a response of CR, PR, and SD at later disease assessments (Week 14 and Week 30) will receive additional doses of loncastuximab tesirine on C5D1, C6D1, C9D1, and C10D1.

During Phase 2 when loncastuximab tesirine is given at every cycle, patients will receive loncastuximab tesirine Q4W on Day 1 of every subsequent cycles starting at C3.

Dose administered at each infusion ( $\mu$ g) for loncastuximab tesirine is calculated by concentrated investigational product (IP) volume (in mL)\* 5 mg/mL \*1000. For incomplete infusion, adjust the calculated prepared dose by multiplying a factor of (1- volume of dosing solution not administered [in mL]/ 50 mL). If volume of dosing solution not administered is missing, then adjust the calculated prepared dose by multiply the factor of (end time – start time [in minutes])/30 minutes.

[figure not shown]

Table 1 Target study day for loncastuximab tesirine

Study Visit	Target Study Day in Phase 1	Target Study Day when Loncastuximab Testirine is Given Intermittently in Phase 2	Target Study Day when Loncastuximab Testirine is Given at Every Cycle in Phase 2
C1D1	1	1	1
C2D1	22	22	22
C3D1	NA	NA	43
C4D1	NA	NA	71
C5D1	99	99	99
C6D1	127	127	127
C7D1	NA	NA	155
C8D1	NA	NA	183
C9D1	NA	211	211

C10D1	NA	239	239
C11D1	NA	NA	267
C12D1	NA	NA	295
C13D1	NA	NA	323
C14D1	NA	NA	351

Note: (1) If patients receive dose beyond C14, target study day at each cycle is calculated by adding 28 days from target study day in previous cycle. (2) Target study day calculation allows +/- 2 days window.

Duration of treatment, number of cycles dosed, total dose received ( $\mu\text{g}$ ), total weight adjusted dose received ( $\mu\text{g}/\text{kg}$ ), average dose per cycle ( $\mu\text{g}/\text{kg}$ ), dose delay, reduction, and interruption, and relative dose intensity for loncastuximab tesirine will be summarized.

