6.2.2 Preparation and Administration

Loncastuximab tesirine solution at the concentration of 5 mg/mL will be the basis for the preparation of the infusion solution. The amount of the product to be prepared will depend on the dose level and the weight of the patient. The weight of the patient at Cycle 1 Day 1 can be used for calculating the dose. If the patient's weight measured on subsequent dosing days has changed by 10% or more compared to the weight used to calculate the previous dose, then the dose should be recalculated based on the new weight. Additional details are included in the pharmacy manual.

Loncastuximab tesirine will be administered as a 30-minute IV infusion. Variations in infusion times due to minor differences in IV bag overfill/underfill, and the institution's procedure for flushing chemotherapy lines will not result in protocol deviations.

Extravasation of loncastuximab tesirine may be associated with local irritation, swelling, pain, or tissue damage. The IV infusion site should be monitored for signs of IV infiltration or drug extravasation, and patients should be instructed to report immediately any signs of IV infiltration or drug extravasation during or after the infusion. Suspected extravasation of loncastuximab tesirine should be managed according to institutional protocol for management of extravasation of cytotoxic chemotherapy. For patients who have a central line, administration of loncastuximab tesirine via this central line should be considered.

Sufficient ibrutinib will be dispensed so each patient can take 560 mg or 420 mg orally once daily until the next visit.

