6.6 Overdose Management

An overdose is any dose of study drug(s) given to a patient that exceeds by 15% of the dose described in the protocol. Any overdose, with or without associated AEs, must be promptly reported to the Sponsor. There are no data available to determine what the effects of overdose of loncastuximab tesirine are and whether they can be reversed. There is no specific experience in the management of ibrutinib overdose in patients. Symptomatic treatment and standard supportive care measures for the management of any observed toxicity should be applied.

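### The time-based fallback for incomplete loncastuximab tesirine infusions in SAP 5.8.1 has no upper limit of 1, so it can credit a patient with more drug than was prepared

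*SAP*

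**What the plan says.** SAP 5.8.1, under loncastuximab tesirine, computes the dose at each infusion from the volume of concentrated product and its 5 mg/mL strength. Two adjustments follow.

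- Volume rule: "For incomplete infusion, adjust the calculated prepared dose by multiplying a factor of (1- volume of dosing solution not administered [in mL]/ 50 mL").
- Time rule, used when that volume was not recorded: "If volume of dosing solution not administered is missing, then adjust the calculated prepared dose by multiply the factor of" elapsed over nominal infusion time, which the SAP writes out as "end time – start time [in minutes])/30 minutes".

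The time rule comes directly after the sentence on incomplete infusions, so I read it as applying to those infusions only. The text gives it no ceiling and does not say how pauses are handled.

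The 30-minute divisor is the nominal infusion time in Protocol 6.2.2: "Loncastuximab tesirine will be administered as a 30-minute IV infusion". The same section tolerates small departures from it: "Variations in infusion times due to minor differences in IV bag overfill/underfill" are not deviations.

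The derived dose supports the SAP 5.8.1 summaries of total dose, weight-adjusted dose and average dose per cycle. Relative dose intensity is also summarised, but the readable text gives no formula for it for this drug.

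Two other places use a 15% margin. SAP 5.3 item 4 lists an incorrect dose as an important deviation, including where "actual dose of study drug was greater than 15% more or less than" the planned dose. Protocol 6.6 says: "An overdose is any dose of study drug(s) given to a patient that exceeds by 15% of the dose described in the protocol".

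**The concern.** An incomplete infusion delivers, by definition, less than was prepared, so its dose factor must lie between 0 and 1. The volume rule respects this for any non-negative leftover volume. The time rule, which estimates the same quantity, does not: it treats every minute between start and end as a minute of delivery at the nominal rate.

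That is reasonable when an infusion is simply stopped early. It fails when an infusion is paused or slowed and then abandoned, because the clock keeps running while little or no drug goes in. The plan allows for such events. SAP 5.8.1 summarises dose interruption, SAP 5.10.1.1 summarises infusion-related reactions, and Protocol 6.2.2 has sites watch for extravasation during the infusion.

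At stake is the accuracy of the exposure tables. The error can run in the wrong direction, so that a patient who received too little appears to have received too much. Phase 1 has tolerability and a recommended dose as its objective, and exposure is part of the context in which those results are read.

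**Working it through.** The documents state no figure for this point, so there is nothing to reproduce. The check is to evaluate the two rules as written.

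**Inputs**

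- Time factor = (end − start)/30, in minutes (SAP 5.8.1).
- Volume factor = 1 − V/50, where V is the volume not given in mL (SAP 5.8.1).
- Nominal infusion time 30 minutes (Protocol 6.2.2).
- Deviation margin 15% above or below plan (SAP 5.3 item 4).
- Planned dose for illustration: 60 µg/kg, the initial recommended dose.

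Assumptions: the prepared dose equals the planned dose. Start and end are the first start and the last stop, so pauses are included. The time spans are illustrative.

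**Step 1: where the time rule leaves the possible range**

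- Factor above 1 when the span exceeds 30 × 1 = 30 minutes.
- Factor above 1.15 when the span exceeds 30 × 1.15 = 34.5 minutes.
- Factor below 0.85 when the span is under 30 × 0.85 = 25.5 minutes.

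**Step 2: credited dose at a planned 60 µg/kg**

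| Span (min) | Factor | Credited (µg/kg) | With cap at 1 (µg/kg) |
|---|---|---|---|
| 25 | 25/30 = 0.83 | 50 | 50 |
| 31 | 31/30 = 1.03 | 62 | 60 |
| 35 | 35/30 = 1.17 | 70 | 60 |
| 40 | 40/30 = 1.33 | 80 | 60 |
| 45 | 45/30 = 1.50 | 90 | 60 |
| 60 | 60/30 = 2.00 | 120 | 60 |

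The size of the error depends on the span. It is a few percent just over 30 minutes and large at 45 or 60.

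**Step 3: the two rules on the same infusion**

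Suppose 10 of 50 mL were left and the span was 45 minutes.

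- Volume factor: 1 − 10/50 = 0.80.
- Time factor: 45/30 = 1.50.
- Ratio: 1.50/0.80 = 1.875.

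If only the leftover volume were missing from the record, the credited dose would be 1.875 times the dose given.

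**Step 4: effect on one patient's total**

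Take a patient with two doses, one full and one as in step 3.

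- As credited: (1 + 1.50)/2 = 125% of plan.
- As given: (1 + 0.80)/2 = 90% of plan.
- With a cap alone: (1 + 1.00)/2 = 100% of plan.

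**Step 5: what a cap does and does not repair**

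The cap removes impossible values but does not recover the dose given: in step 3 it yields 1.00 against 0.80. Removing pauses does more. At the nominal rate, 40 of 50 mL takes 0.80 × 30 = 24 minutes, so the 45-minute span would contain 45 − 24 = 21 minutes of pause, and 24/30 = 0.80 is the correct factor. If the infusion was slowed rather than paused, removing pauses does not help and the capped value is only an upper bound.

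**The case against.** The strongest case against acting has four parts.

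*Rarity.* Three things must coincide: an incomplete infusion, no recorded leftover volume, and a span over 30 minutes. An infusion stopped early has a short span, where the rule works as intended. One that is slowed but finished is not incomplete. The Protocol 6.2.2 allowance concerns minor timing variation from bag fill and line flushing, and is not evidence of long interrupted infusions. This stands. The documents give no count of such infusions.

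*Data review.* SAP 8.1.1 says that data that look wrong will be queried, and SAP 5.8.1 has infusion details listed. A dose above 100% for an incomplete infusion should be noticed. This stands in part. Review may find the record, but the SAP then gives no other rule for the value to use.

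*Missing figure.* A figure after the formula is not shown, so a limit there cannot be wholly excluded. The sentence that gives the rule is nevertheless complete without one.

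*Consequences.* A reader might infer that a span over 34.5 minutes produces a false overdose deviation, removes the patient from the Per Protocol Set, and so disturbs the primary efficacy analysis. The documents do not support that chain.

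- SAP 5.3 item 4 does not say that the actual dose is the one derived in 5.8.1. It says deviations "will be agreed upon by a review of individual subject data", which could clear a false flag.
- The Protocol 6.6 overdose definition concerns a dose given to a patient, not a derived value.
- SAP 5.1.6 excludes patients with major deviations from the Per Protocol Set. SAP 5.3 gives item 4 in a list of important reportable deviations and does not equate the two.
- SAP 5.9 defines the primary efficacy analysis in the every-cycle cohort, which SAP 4 says will not be enrolled. SAP 5.9 also bases efficacy on the Efficacy Analysis Set, with the Per Protocol Set as an addition.

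**Conclusion.** The defect is real but small. As written, the time rule credits an incomplete infusion with more than the prepared dose whenever its start-to-end span exceeds 30 minutes, and the SAP's own volume rule cannot do this. Total dose, weight-adjusted dose and average dose per cycle are inflated for the patients concerned. Relative dose intensity is inflated so far as it is built on dose received. Patients in Phase 1 and in the intermittent Phase 2 cohorts are exposed to this, because they are the ones treated.

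The consequence shown is limited to descriptive exposure summaries, probably for few patients. A false flag under the 15% criterion remains possible, but only if the deviation check uses the derived dose. No effect on the primary efficacy analysis is shown.

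The conclusion assumes that start and end times include pauses and that the figure not shown contains no cap. The percentages compared with plan also assume that the prepared dose equals the planned dose.

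**What to change.** In SAP 5.8.1, replace the fallback with three steps.

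1. Query the site for the missing leftover volume and use the volume rule if it is supplied.
2. If it stays missing, multiply the prepared dose by min(1, minutes of actual infusion excluding recorded interruptions / 30).
3. Flag in the exposure listing every record where the cap applies, since the capped value is an upper bound and not an estimate.

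It would also help to state in SAP 5.3 item 4 whether the actual dose there is the derived dose or the dose reported by the site.

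The cost is about one line of SAP text and of derivation code, plus a few queries. The small downside is that capped records may still overstate the dose received. This concerns data derivation only and implies nothing about how the drug should be given.
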